9.6 Pharmacodynamics

9.7 Pharmacogenomics

9.8.1 Additional Research Collection

This protocol will include residual sample storage for additional research (AR).

For All US sites:

Additional research is required for all study participants, except where prohibited by IRBs/ethics committees or academic/institutional requirements. Where one or more of these exceptions occurs, participation in the additional research should be encouraged but will not be a condition of overall study participation.

If the IRB/ethics committees and site agree to the mandatory additional research retention and/or collection, then the study participant must agree to the mandatory additional research as a requirement for inclusion in the study.

If optional participation is permitted and approved, then the study participants may opt out of the additional research retention and/or collection.

For non-US Sites

Additional research is optional for all study participants, except where retention and/or collection is prohibited by local laws or regulations, ethics committees, or institutional requirements.

This collection for additional research is intended to expand the translational R&D capability at Bristol-Myers Squibb, and will support as yet undefined research aims that will advance our understanding of disease and options for treatment. It may also be used to support health authority requests for analysis, and advancement of pharmacodiagnostic development to better target drugs to the right patients. This may also include genetic/genomic exploration aimed at exploring disease pathways, progression and response to treatment etc.

Sample Collection and Storage

All requests for access to samples or data for additional research will be vetted through a diverse committee of the study Sponsor's senior leaders in Research and Development (or designee) to ensure the research supports appropriate and well-defined scientific research activities.

Residual P will also be retained for additional research purposes.

Samples kept for future research will be stored at the BMS Biorepository in USA or an independent, BMS-approved storage vendor.

The manager of these samples will ensure they are properly used throughout their usable life and will destroy the samples at the end of the scheduled storage period, no longer than fifteen (15) years after the end of the study or the maximum allowed by applicable law.

Transfers of samples by research sponsor to third parties will be subject to the recipient's agreement to establish similar storage procedures.

Samples will be stored in a coded fashion, and no researcher will have access to the key. The key is securely held by the Investigator at the clinical site, so there is no direct ability for a researcher to connect a sample to a specific individual.

Further details of sample collection and processing will be provided to the site in the procedure manual.

| Table 9.8.1-1: Residual Sample Retention for Additional Research Schedule |
|---|
|---|

| Sample Type | Timepoints for which residual samples will be retained |
|-------------|--|
| PK Serum | All |
| | |
| | |
| | |
| | |
| | |
| | |
| | |

Abbreviations:

[figure not shown]
9.8.2 Tissue Specimens

[figure not shown]
Pre-treatment tumor tissue specimens, not previously irradiated ("not previously irradiated" applies to participants with unresectable/metastatic disease recurrence entering open-label nivolumab), in the form of a paraffin embedded block to contain sufficient tissue for at least 15 sections or a minimum of 15 unstained slides, preferably freshly cut, from the primary diagnostic biopsy must be shipped to the central lab prior to randomization or treatment assignment, for

blinded or open-label nivolumab treatment, respectively. If a minimum of 15 unstained slides or 1 FFPE block cannot be provided, the eligibility should be discussed with the Medical Monitor or designee. This minimum quantity applies to tissue obtained prior to randomization/assignment to the open label portion as well as tissue obtained upon disease recurrence or progression.

The following tissue attributes for the samples prior to randomization of participants with Stage IIB/C melanoma are not mandatory, but considered desirable to optimize downstream analyses. The tissue biopsy samples should be from the primary diagnostic material (obtained for example by biopsy punch, shave, excision, incision, saucerization). If tissue from the primary diagnostic biopsy is insufficient, it may be supplemented by tissue from subsequent surgeries, provided at least 3 mm of tumor in smallest dimension is present. A dermatopathologist's review/input is encouraged. Pathology samples acquisition guidelines and submission process will be outlined in the study Laboratory Manual.

9.10 Other Assessments

Not applicable.

10 STATISTICAL CONSIDERATIONS

10.1 Sample Size Determination

10.1.1 RFS

The sample size of the study is based on a comparison of the RFS distribution between participants randomized to nivolumab and participants randomized to placebo.

| Sampl | e size calculations | for this study design | were done using EAST |
|-------|---------------------|-----------------------|----------------------|

(v 6.4.1).

For this comparison of RFS between nivolumab and placebo in all randomized participants, approximately 154 RFS events would be required for a two-sided experiment-wise alpha = 0.05 log-rank test, to show a statistically significant difference in RFS between the treatment arms with at least 90% power when the average hazard ratio (HR) of the nivolumab arm to the placebo arm

[figure not shown]
Final analysis of RFS will be conducted when approximately 154 RFS events have occurred.

One interim analysis of RFS will be conducted when approximately 123 RFS events (80% information fraction) have been reached among all randomized participants.

[figure not shown]
10.1.2 Overall Survival

OS will be formally compared only if the null hypothesis for the primary endpoint (RFS) is rejected.

For the comparison of OS between nivolumab and placebo in all randomized participants, approximately 277 deaths would be required for a two-sided experiment-wise alpha = $0.05 \log$ rank test, to show a statistically significant difference in OS with at least 79.6% power

Although formal OS testing is planned at OS FA, descriptive statistics for OS will be prepared at RFS IA and/or RFS FA **Sector**. If OS results (beyond the frequency of deaths per arm) including Kaplan-Meier (KM) curves are requested, an administrative alpha of 0.0001 will be spent as alpha penalty. Should such analyses be conducted, only a BMS restricted team will have access to OS descriptive results.

10.2 Populations for Analyses

| Description |
|--|
| All participants who signed an informed consent form and were registered into the IRT. |
| All participants who were randomized to any treatment arm in the study. |
| All participants who received at least one dose of study drug. |
| All treated participants with available serum time- concentration data. |
| |
| All treated participants with baseline and at least 1 post baseline pre-infusion nivolumab immunogenicity assessment |
| |

For purposes of analysis, the following populations are defined:

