| Other | | |
| | | |
| IRT Call/Assignment | X | |

Abbreviations: CT, computed tomography; eCRF, electronic Case Report Form; FFPE, formalin-fixed paraffin embedded; FSH, follicle-stimulating hormone; ID, IRT, Interactive Response Technology; MRI, magnetic resonance imaging; SAE, serious adverse events; SAR-CoV-2, severe acute respiratory syndrome coronoavirus 2; WOCBP, women of childbearing potential.

^a Some of the assessments referred to in this section may not be captured as data in the eCRF. They are intended to be used as safety monitoring by the treating physician. Additional testing or assessments may be performed as clinically necessary or where required by institutional or local regulations.

^b For participants who opt for open-label on-protocol nivolumab treatment after first disease recurrence, Screening assessments will occur prior to assignment to optional on-protocol open-label nivolumab treatment.

| Table 2-2: | On-Treatment Assessments CA20976K (Applies to All Participants: Blinded or Open-label Treatment) |
|------------|---|
| 10010 1 10 | |

| Procedure ^{a,b} | Each cycle = 4 weeks) ^c | Notes Cycle 1 is to be initiated within 3 calendar days (72 hours) of randomization. ^d Subsequent cycles can be initiated within ± 3 days of the target visit date. See Section 7 (Treatment) for further details. | | | | |
|---|---|--|--|--|--|--|
| | Day 1 of Each Cycle | | | | | |
| | Cycle | | | | | |
| Safety Assessments | | | | | | |
| Targeted Physical Examination | X | To be performed within 72 hours prior to dosing. Pay special attention to skin and nodal examination. | | | | |
| Vital Signs | X | Include BP, heart rate, temperature. | | | | |
| Weight and Performance Status | X | Within 72 hours prior to dosing. | | | | |
| Adverse Event Assessment (including SAE assessment) | X | Continuously during treatment (including AEs/SAEs associated with SARS-CoV-2 infection). All AEs/SAEs are to be graded and managed per NCI CTCAE v5. | | | | |
| Review of concomitant medications | X | | | | | |
| Laboratory Tests | X | See full list of assessments in Section 9.4.4. | | | | |
| | | On site/local labs to be performed within 72 hours prior to dosing. | | | | |
| | | Note: Cycle 1 Day 1 laboratory tests are not required to be repeated if performed within 14 days prior to first dose. | | | | |
| | | Amylase, lipase, albumin, ACTH, and cortisol as clinically indicated. | | | | |

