| Abbreviations: AE. adverse event: BMS. Bristol-Mvers Sauibb: CR. complete response : CT. computed tomography: FU1, Follow-Up Visit 1; FU2, Follow-Up Visit 2; MRI, magnetic resonance imaging; NCI CTCAE v5, National Cancer Institute Common Terminology Criteria for Adverse Events version 5; OS, overall survival; PK, pharmacokinetics; PR, partial response; SAE, serious adverse event; SD, stable disease. | | | | |
| ^a Participants must be followed for at least 100 days after the last dose of study treatment. FU1 should occur 30 days from the last dose (± 7 days) or can be performed on the date of discontinuation if that date is greater than 37 days from the last dose. FU2 occurs approximately 100 days (± 7 days) from the last dose of study treatment. Both follow-up visits should be conducted in person. | | | | |
| If a participant on the placebo arm experiences recurrence, and opts to receive open-label nivolumab monotherapy (Arm 1 or 2), participants may or may not | | | | |

⁷ If a participant on the placebo arm experiences recurrence, and opts to receive open-label nivolumab monotherapy (Arm 1 or 2), participants may or may not have completed the two follow-up visits (FU1 and FU2) on blinded treatment. Assessments from FU1 and FU2, if conducted, may contribute to satisfying screening/Cycle 1 Day 1 requirements prior to treatment assignment (please check Screening Schedule of Activities requirements). If the participant (nivolumabor placebo-treated) does not opt to receive open-label nivolumab treatment, the assessments/assessment frequency described in this table apply. For optional open-label nivolumab treatment after first recurrence, visits after FU2, may be accomplished by visit (eg, examination, laboratory tests) OR by phone contact.

^c Timing is calculated from the date of the first dose of blinded study treatment, or open-label nivolumab treatment, whichever is applicable.

- ^d Efficacy Assessments (Arm 1: Resectable disease): If a participant starts systemic therapy for melanoma recurrence or for a new non-melanoma cancer after study drug discontinuation, follow-up scans can be done as per standard of care. Participants who did not have Stage IV resected disease on entry in the open-label treatment portion of the trial who develop a loco-regional recurrence only and have not initiated subsequent anticancer systemic therapy, must be followed by surveillance imaging until the development of distant metastases.

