6.1.2 Inclusion Criteria for Participants Receiving Treatment after Recurrence

1) Signed Written Informed Consent

a) Participants must have signed and dated a separate IRB/IEC approved written informed consent form for open-label treatment with nivolumab monotherapy in accordance with regulatory and institutional guidelines. All other informed consent related details discussed in Section 6.1.1 for participants receiving blinded treatment apply to participants receiving treatment after recurrence.

2) Type of Participant and Target Disease Characteristics

- a) Participant must have been randomized, treated and have documented recurrence (per Section 9.1.2.1) of melanoma on blinded nivolumab or placebo treatment
- b) Recurrent disease must have been diagnosed within 3 years of last dose of blinded study. Participants assigned to blinded nivolumab treatment must have completed 1 year of therapy and have experienced disease recurrence more than 6 months following the last dose.
- c) Participant must not have received any other systemic anticancer therapy (including investigational anticancer therapy) or loco-regional anticancer therapy (other than surgery for complete resection of the recurrence and radiation therapy administered with a palliative intent) between the last dose of blinded study treatment and the first dose of open-label study treatment.

NOTE: Prior adjuvant radiation therapy (RT) after neurosurgical resection for central nervous system (CNS) lesions or prior RT to CNS metastases is allowed.

- d) Palliative/definitive radiotherapy, if administered, must have been completed at least 2 weeks prior to study drug administration
- e) Arm 1 (resectable disease only): Complete documented resection of recurrent disease (preferably within 12 weeks prior to assignment to open-label treatment) with margins negative (per local standard) for disease. For CNS lesion(s), documentation indicating that there has been complete resection of CNS lesion(s) will suffice as confirmation of negative margins.

NOTE: A copy of the de-identified pathology report(s) confirming negative margins on the resected specimen must be sent to the Central Laboratory vendor prior to assignment to open-label treatment.

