If the infusion was interrupted, the interruption details will also be documented on the CRF. Blood samples will be processed to collect serum and stored preferably at -70°C (samples may be stored at -20°C up to 2 months). Further details of pharmacokinetic sample collection and processing will be provided to the site in the lab manual. The serum samples will be analyzed for drug (nivolumab) and ADA (anti-nivolumab antibodies) by validated immunoassays. Samples with a positive ADA response may also be analyzed for neutralizing ADA response to nivolumab.

In addition, selected serum samples may be analyzed by an exploratory method that measures nivolumab, or detect anti-drug antibodies for technology exploration purposes; exploratory results will not be reported. The corresponding serum samples designated for either PK, immunogenicity assessments may also be used for any of those analyses, if required (eg, insufficient sample volume to complete testing or to follow-up on suspected immunogenicity related AE).

Table 9.5-1:Pharmacokinetic (PK) and Immunogenicity Sampling Collections for Blinded Nivolumab or Placebo-
Treated Participants or Participants Treated with Open-Label Nivolumab After First Recurrence

| Study Day ^a (1 Cycle = 4 weeks) | Time (Relative To Dosing) Hour | Time (Relative To Dosing) Hour: Min | Pharmacokinetic Serum Sample for Nivolumab | Immunogenicity Serum for Nivolumab |
|---|-----------------------------------|---|--|--|
| Cycle 1 Day 1 | Predose ^b | 0:00 | Х | Х |
| | End of Infusion ^c | 0:30 | Х | |
| Cycle 2 Day 1 | Predose ^b | 0:00 | Х | Х |
| Cycle 3 Day 1 | Predose ^b | 0:00 | Х | Х |
| Cycle 6 Day 1 | Predose ^b | 0:00 | Х | Х |
| | End of Infusion ^c | 0:30 | Х | |
| Cycle 9 Day 1 | Predose ^b | 0:00 | Х | Х |
| FU1 First 2 Follow-up visits $(30 \pm 7 \text{ days from the} \text{ discontinuation of study drug})$ | N/A | N/A | Х | Х |
| FU2 First 2 Follow-up visits $(100 \pm 7 \text{ days from the} \text{ discontinuation of study drug})$ | N/A | N/A | Х | Х |

Abbreviation: FU1, Follow-Up Visit 1; FU2, Follow-Up Visit 2; Min, minutes.

^a If a participant discontinues study drug treatment during the treatment/sampling period, they will move to sampling at the follow-up visits.

[figure not shown]

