^b Predose samples should be collected immediately before the administration of the drug (preferably within 30 minutes). If it is known that a dose is going to be delayed, then the predose sample should be collected immediately prior to the delayed dose. However, if a predose sample is collected but the dose is subsequently delayed, an additional predose sample should not be collected.

^c The end of infusion-PK sampling (EOI-PK) occurs when the entire nivolumab dose in the infusion bag is administered to the patient. If diluent will not be administered to flush the IV lines, this sample should be taken immediately prior to stopping the IV infusion (preferably within 2 minutes prior to the end of infusion). If diluent is used to flush the dose remaining in the infusion line, then the EOI-PK sample will occur when there is no dose remaining in the infusion line after a flush. If the end of IV infusion is delayed to beyond the nominal infusion duration, the collection of this sample should also be delayed accordingly.

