10.3 Statistical Analyses

The statistical analysis plan (SAP) will be developed and finalized before the first database lock for formal interim efficacy analysis, and will describe the selection of participants to be included in the analyses, and procedures for accounting for missing, unused, and spurious data. Below is a summary of planned statistical analyses of the primary and secondary endpoints.

A description of the participant population will be included in a statistical output report, including subgroups of age, gender and race.

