10.3.3.5 Immunogenicity Analyses

Methodology for analysis of immunogenicity will be described in the statistical analysis plan.

10.3.3.6 Analyses of Follow-Up Data from Participants Receiving Optional Open-Label Nivolumab Treatment

Methodology for analysis of follow-up data from participants receiving optional open-label nivolumab treatment will be described in the statistical analysis plan.

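### As worded, the immunogenicity population in Section 10.2 leaves out nivolumab participants whose only post-baseline ADA samples come from the follow-up visits

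*Combined protocol and SAP*

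**What the plan says.** Section 10.2 of the protocol sets the membership rule for immunogenicity: "All treated participants with baseline and at least 1 post baseline pre-infusion nivolumab immunogenicity assessment". One dose is enough to be treated. The PK population in the same table asks only for usable concentration data and has no pre-infusion condition.

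Table 9.5-1 (Section 9.5) lists the ADA draws. There is a baseline predose draw at Cycle 1. Post-baseline draws follow before dosing at Cycles 2, 3, 6 and 9, and again at Follow-up Visit 1 (FU1) and Follow-up Visit 2 (FU2), where the time relative to dosing is given as not applicable. Footnote a covers early stoppers: "If a participant discontinues study drug treatment during the treatment/sampling period, they will move to sampling at the follow-up visits". Section 9.5 has the serum assayed for ADA without excepting the follow-up samples; only placebo samples go unanalysed.

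Two passages leave details to the SAP. Section 10.3 says that it "will describe the selection of participants to be included in the analyses", and Section 10.3.3.5 says: "Methodology for analysis of immunogenicity will be described in the statistical analysis plan". Nothing in the text reviewed says that an FU1 or FU2 sample satisfies the post-baseline requirement.

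**The concern.** The sampling schedule and the population rule pull in different directions. The schedule sends a participant who stops early to FU1 and FU2 for ADA sampling. The rule accepts only samples that precede an infusion. Whether a participant is evaluable then depends on reaching a second infusion visit, not on having a usable post-baseline ADA result.

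The protocol's own rules can produce such participants. Under Table 7.4.1-1, a Grade 3 or 4 infusion or hypersensitivity reaction ends treatment permanently; if it occurs at the first dose, no Cycle 2 predose draw need follow. Under Section 9.5, when a delay is known in advance the predose sample waits for the delayed dose; if that dose is never given, the sample may never be taken.

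What is at stake is the denominator of the ADA incidence, and the incidence itself if ADA positivity differs between those retained and those left out. Exclusion is tied to stopping early, so it cannot be assumed to be random. That is not a claim that ADA cause early stopping.

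**Working it through.** **1. Which timepoints can qualify a participant**

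The post-baseline ADA timepoints in Table 9.5-1 are Cycle 2, Cycle 3, Cycle 6, Cycle 9, FU1 and FU2, six in all. The first four precede an infusion. FU1 and FU2 do not, so 2 of 6 cannot qualify anyone under the literal rule.

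For a nivolumab participant with one dose, a baseline sample and no Cycle 2 draw:

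- qualifying samples under the Section 10.2 wording: 0, so excluded;
- qualifying samples if FU1 and FU2 count: up to 2, so included.

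**2. Whether timing justifies the distinction**

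- Cycle 2 predose, on time: cycles are 4 weeks long and Table 2-2 states "Subsequent cycles can be initiated within ± 3 days of the target visit date". That gives 28 ± 3, or days 25–31 after the first dose.
- FU1 after a single dose: Table 2-3, footnote a, places it at 30 ± 7 days from the last dose, or days 23–37. It may be done on the discontinuation date if that is later than day 37.
- FU2: 100 ± 7, or days 93–107.

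The on-time Cycle 2 window lies wholly inside the FU1 window. Two participants can give serum at the same interval after the same single dose, and only the one who came for an infusion visit qualifies. Table 9.5-1 counts FU1 from discontinuation of study drug instead of from the last dose. If discontinuation is decided later, FU1 moves later and the overlap can vanish, so the statement is that the two samples can coincide, not that they always do.

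**3. Whether open-label sampling brings these participants back**

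It does not for those randomised to nivolumab. Section 6.1.2 requires: "Participants assigned to blinded nivolumab treatment must have completed 1 year of therapy". A participant who stopped after one dose cannot enter the open-label part and so gets no later predose draw there.

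**4. Possible size**

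The documents give no early-stopping, sample-attendance or ADA rate, and the sample size is blacked out. All inputs here are assumptions:

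- e = share of nivolumab participants with no post-baseline predose ADA sample, 1–4%;
- r = share of those with a baseline sample and an FU1 or FU2 sample, 50–90%;
- p0 = ADA positivity in those retained, 5%;
- p = ADA positivity in those left out, 0–15%.

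The formula takes everyone with a predose sample as having a baseline. The recoverable group, as a share of the enlarged population, is q = e·r / (1 − e + e·r). The change in incidence is q·(p − p0).

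| e | r | q | shift if p = 0% | shift if p = 15% |
|---|---|---|---|---|
| 1% | 50% | 0.005/0.995 = 0.50% | −0.03 | +0.05 |
| 2% | 75% | 0.015/0.995 = 1.51% | −0.08 | +0.15 |
| 4% | 90% | 0.036/0.996 = 3.61% | −0.18 | +0.36 |

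Shifts are in percentage points. At the largest share, incidence would be 4.82% to 5.36% instead of 5.0%. If p = 5% the shift is zero throughout. A 1-point shift at q = 3.61% would need a positivity gap of 1/0.0361 = 27.7 points.

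**The case against.** The strongest objection is that the operative rule may sit in the SAP. Sections 10.3 and 10.3.3.5 hand participant selection and immunogenicity methods to it, and its immunogenicity text was not available here. The table in Section 10.2 is also damaged: the column of population names is missing and there are blank rows around the quoted one. This stands as a limit. The SAP may already count follow-up samples. Section 10.2 nevertheless states a definition of its own. If the SAP departs from it, the two need aligning; if the SAP repeats it, the exclusion takes effect.

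Second, the pre-infusion condition may be there only to keep out end-of-infusion serum, since Section 9.5 lets PK serum stand in for immunogenicity testing when needed. That is plausible, but the words also shut out FU1 and FU2, and the end-of-infusion exclusion can be stated directly. Requiring an on-treatment sample could also be a deliberate choice for an exploratory summary, but no such reason is given.

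Third, the affected group is small. A single predose draw at Cycle 2, 3, 6 or 9 is enough to qualify. A Cycle 2 sample drawn before a dose that was then delayed and never given can also count, since Table 9.5-1, footnote b, treats it as the predose sample: "However, if a predose sample is collected but the dose is subsequently delayed, an additional predose sample should not be collected". The rule governs membership only; ADA results from those left out are still assayed and available individually. All of this is accepted.

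Fourth, the numerical range rests entirely on assumed inputs. That is also accepted; the range shows only that the effect is likely to be small.

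**Conclusion.** The point holds as a matter of wording. Taken literally, Section 10.2 excludes a nivolumab participant who has a baseline ADA sample and one or both follow-up samples but no post-baseline predose draw, although the schedule directs early stoppers to exactly those follow-up samples.

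The consequence is minor. It touches only the denominator and incidence of an exploratory endpoint. The change in incidence is probably well under 1 percentage point, may be zero, and has no known direction. RFS, OS and the all-treated safety analysis do not change. Confidence is medium, because the SAP may already settle the matter. This is an inexpensive improvement, not a threat to the trial's conclusions.

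**What to change.** Reword the Section 10.2 entry so that membership requires treatment, a baseline ADA assessment, and one or more later ADA assessments from serum drawn either before an infusion or at Follow-up Visit 1 or 2. State explicitly that end-of-infusion serum does not qualify. Use the same definition in the SAP. If the SAP already counts follow-up samples, only the Section 10.2 sentence needs to change.

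The cost is one sentence and a consistency check. The FU1 and FU2 samples are already scheduled, so there are no extra visits or draws. The denominator grows only by participants with a baseline sample and a follow-up sample. Participants with no baseline sample, or with no post-baseline sample of any qualifying kind, stay out under either wording, so some selection remains.
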